4.6.3 Further Exploratory endpoints

Factors that may affect the SARS-CoV-2 infection or COVID-19 disease such as sex, age, BMI, and SARS-CoV-2 variant type will be assessed with a logistic regression model with proportion of COVID-19 infections as dependent variable and treatment as independent variable and the factors as covariates. Odds-ratios, 95% CI and P-values will be presented.

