	If the close contact wishes to participate in the study, they should ask the primary contact if they agree to give their informed consent by signing the form attached to the leaflet, through which primary cases agree that information related to their positive testing will be collected as evidence. Then, the contact case should get in touch with the study site and arrange for an appointment for the screening visit (within 5 days after the contact with the index case). At that appointment the contact will be screened, and they will provide the study staff with the index case's signed consent form and positive PCR test result. In addition, informed consent from the close contact must be obtained. If all eligibility criteria are met, the participant (close contact) will be randomised and a loading treatment dose will be administered. Participants will be assigned in a 1:1 ratio to receive oral daily treatment with either ivermectin or placebo. The study requires two visits to the study centre, on Day 1 and Day 28, the first and last days of treatment. In addition, there will be at least 3 remote visits that can be conducted by telephone. The treatment period lasts for 28 days in total, followed by a 28-day follow-up period, and there is a 2-day window period for visits. Therefore, total study duration for each participant is up to 58 days.			
Study Population:	Healthy volunteers between 18 and 65 years old, self-isolating after being in close contact with an individual who has had a documented exposure to COVID-19 within a maximum of 5 days prior to Screening.			

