The number/frequency of participants with TEAEs, related TEAEs, PTAE, the number/frequency of participants with related PTAEs, SAEs and CTCAE grade 3 or more will be displayed by system organ class and preferred term according to MedDRA classification. The frequency of participants with at least one TEAE, PTAE, related PTAE, SAE and/or AE of CTAE grade 3 or more will be compared between treatment groups using a chi-squared test or a Fisher exact test.

Table 1: Schedule of Assessments

	Pre Screening D-1 or D1*	Screening & Randomisation	On-treatment period (i)				EOS (J)
		D1	D4 (±1 day)	D7 (±1 day)	D10 (±1 day)	EOT-D28** (+2 days)	D56 (±2 days)
	Remote	On-site Visit***	Remote	Remote	Remote	On-site Visit***	Remote
Study participation suitability questionnaire (a)	X						
ICF signature (b)		X					
Demographics		X					
Medical history		X					
I/C criteria		X					
Treatment dispensation		X					
Treatment administration (c)						-	
RT-PCR test (d)		X	X	X	X	X	
Antigen test (e)		X					
Serology (f)		X				X	X
NEWS-2 scale		X			X	X	
COVID-19 WHO scale		X			X	X	
Laboratory tests (g)		X				X	X
Urine pregnancy test (g)		X				X	X
Randomisation		X					
Participant diary (i)						•	
ECG		X				X	
Vital signs		X			X	X	
Adverse Events			· -				
Concomitant medication							

Clinical Protocol

- * Pre-Screening corresponds to the time frame when the first positive case is detected in the cluster within 5 days prior to screening. The study is immediately proposed to the exposed cluster members who might potentially meet the eligibility criteria (Note: only one member in the same household will be enrolled).
- ** Preferred on-site visit but can be performed remotely according to the investigator's opinion.
- *** In case of on-site visit, participants should only use private transport. Moreover, a specific room for participants has to be available and restricted to participants in order to limit their contact with patients.
- a) Participants will be questioned about their close contact to the COVID-19 index case, their interest in participating in the study, and will be given information about the study (note that full eligibility inclusion/exclusion criteria will be confirmed once the participant has signed an ICF).
- (b) ICF signature for the participant and the index case to collect information regarding his/her SARS-CoV-2 RT-PCR test results,

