- (c) IMP will be administered as follows: 200 µg/kg as the loading dose admisnistered on D1at the study site, and then 100 µg/kg/day for 27 days taken by the participant at home.
- (d) PCR test to be performed on D1, D4, D7, D10 and D28: sequencing and viral load. In addition, any unscheduled test performed by the participant during the study will also be collected. Confirmed negative participants at baseline will continue RT-PCR testing, as per schedule of assessments, until they become positive or reach the planned end of study. When RT-PCR positivity is confirmed, participant will self-isolate according to local requirements.
- (e) Participants who have been tested positive at the screening with a quick antigen test will be screen failed. In addition, any unscheduled test performed by the participant during the study will also be collected,
- (f) Serology COVID-19 (antibodies levels). In addition, any unscheduled test performed by the participant during the study will also be collected).

(g) Haematology, Biochemistry, Urine pregnancy test,	for details on the parameters evaluated. Pregnancy testing must be highly sensitive, at leas
before first administration.	-

- (i) Participants will receive their diary on D1 and keep it for the duration of the treatment to record data collected between D1 and D28. They will bring it back to the site on D28.
- (J) Additional follow-up remote or on-site unscheduled visits, may be required if deemed necessary by the investigator, notably in case of emerging or prolonged adverse events. During the unscheduled visit, the investigator will evaluate the WHO COVID-19 scale and the NEWS-2 scale, in addition to any assessments deemed necessary.

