3.3 Full Analysis Set

The Full Analysis Set (FAS) includes all participants randomly assigned to a treatment group having received at least one tablet of the study drug (ivermectin or placebo) and having at least one efficacy assessment after randomisation.

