3.4 Modified Full Analysis Set

Modified FAS (mFAS) includes all FAS participants with a confirmed negative SARS-CoV-2 RT-PCR test at baseline.

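### SAP 4.6.3 uses SARS-CoV-2 variant type as a covariate in a model for infection, although a variant is recorded only for participants who became infected

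*SAP*

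**What the plan says.** SAP 4.6.3 lists "Factors that may affect the SARS-CoV-2 infection or COVID-19 disease such as sex, age, BMI, and SARS-CoV-2 variant type" and assesses them in a logistic regression "with proportion of COVID-19 infections as dependent variable and treatment as independent variable and the factors as covariates". It promises odds ratios, 95% confidence intervals and p-values, with no exception for variant. It names no analysis set, gives no rule for participants without a variant, and does not say whether the factors enter together or one at a time.

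The source of variant data is Protocol Table 1, footnote (d): "PCR test to be performed on D1, D4, D7, D10 and D28: sequencing and viral load". The same footnote has baseline-negative participants tested "until they become positive or reach the planned end of study".

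The primary analysis set is the mFAS (SAP 3.4): "Modified FAS (mFAS) includes all FAS participants with a confirmed negative SARS-CoV-2 RT-PCR test at baseline". The wider FAS (SAP 3.3) requires at least one tablet taken and "having at least one efficacy assessment after randomisation", but no negative baseline PCR.

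For the index case, the synopsis (Study Design) says that "information related to their positive testing will be collected as evidence", and Table 1, footnote (b), refers to consent by the "index case to collect information regarding his/her SARS-CoV-2 RT-PCR test results". Neither place mentions the index case's variant, and neither excludes it.

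On missing data, SAP 4.1.2 applies an observed-cases approach in general and restricts multiple imputation to the primary endpoint.

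**The concern.** A covariate in a model for infection must have a value for participants with and without infection. Sex, age and BMI do. A variant obtained by sequencing a participant's own sample does not: someone who never turns positive has no virus to sequence. In the mFAS, variant is a property of the outcome rather than a predictor of it.

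At stake is whether 4.6.3 can deliver its promised output. If the factors enter jointly, which is the natural reading, variant can take the treatment, sex, age and BMI estimates down with it. The analyst would then have to choose a repair after seeing the data, which a pre-specified plan is meant to prevent.

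**Working it through.** **Inputs.** Infection 54% on placebo and a 20-point difference, so 34% on ivermectin; two-sided 5% level; 90% power; 138 evaluable per arm; 30% not evaluable (Protocol synopsis, Statistical Methods; SAP 1.4).

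**The plan's own figures reproduce.** With d = 0.20 and mean proportion 0.44, A = [1.960·√(2·0.44·0.56) + 1.282·√(0.54·0.46 + 0.34·0.66)]² ≈ 5.09. The Casagrande-Pike formula A·[1 + √(1 + 4d/A)]²/(4d²) gives 137.2, rounded up to 138. Then 138/0.70 = 197.1, rounded up to 198 per arm. The odds ratio is (0.54/0.46)/(0.34/0.66) = 2.28. Nothing here is in dispute.

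**Expected counts.**

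| | Infected | Not infected |
|---|---|---|
| Placebo | 138 × 0.54 = 74.5 → 75 | 63 |
| Ivermectin | 138 × 0.34 = 46.9 → 47 | 91 |
| Total | 122 | 154 |

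No variant: 154/276 = 55.8%.

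**Handling 1: drop participants without a variant** (one reading of the observed-cases rule). This leaves 122 events and 0 non-events. The outcome is constant and nothing can be estimated, including treatment.

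**Handling 2: code the uninfected as having none, all infections sequenced.** Take intercept −0.5, +1 on each variant indicator and 0 on every other term. The linear predictor is +0.5 for all 122 infected and −0.5 for all 154 uninfected. Multiplying these coefficients by any larger constant raises the likelihood, so there is complete separation and no finite maximum. A fit with simulated sex, age and BMI and two variants behaved accordingly: variant log-odds of 13.1, 23.1 and 43.1 after 5, 10 and 20 iterations, and a treatment coefficient of 0.00 with a standard error of about 3,600 at the last of these.

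**Handling 3 (illustrative): a fraction q of infections is sequenced and everyone else is coded none/unknown.** The documents give no sequencing rate, so q is an assumption, taken to be the same in both arms. Every variant category still has 0 non-events, so no variant odds ratio is finite. The treatment odds ratio comes only from the unsequenced infections, 47(1−q) and 75(1−q), against 91 and 63 uninfected. The odds ratio (ivermectin vs placebo) is (47/91)/(75/63) = 0.434 throughout, and the interval is exp{ln 0.434 ± 1.96·SE}, with SE = √(1/a + 1/91 + 1/b + 1/63) for a ivermectin and b placebo infections.

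| Model | a | b | Infections used | 95% CI |
|---|---|---|---|---|
| Variant left out | 47 | 75 | 122 | 0.27–0.71 |
| q = 0.9 | 4.7 | 7.5 | about 12 | 0.13–1.44 |
| q = 0.8 | 9.4 | 15 | about 24 | 0.18–1.04 |
| q = 0.6 | 18.8 | 30 | about 49 | 0.22–0.84 |

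Counts are expected values, hence not whole numbers.

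**Contrast.** On the same simulated data, leaving variant out gave an ordinary fit (standard error of the treatment log odds ratio 0.25). Giving every participant a variant unrelated to outcome gave a finite variant coefficient with standard error 0.25. The failure therefore comes from how variant is defined, not from the sample size.

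**Would the FAS help?** Participants PCR-positive on D1 could be sequenced, but they were never at risk of a first infection. Counted as infections, they leave the separation unchanged. Counted as non-events, they give a finite contrast of prevalent with incident infection, which is not the question.

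**The case against.** The strongest reply is that the premise rests on silence. The available protocol text is the synopsis and the schedule of assessments, and SAP section 6.1, which SAP section 4 cites for derived data, is not in the available text. A variant that affects whether a contact is infected is naturally the one they were exposed to. Every participant has a PCR-confirmed index case who consents to collection of test information. An index-case variant would make the model workable. This stands as a limit on the claim: no available passage gives uninfected participants a variant, but one could be defined elsewhere. It does not rescue 4.6.3 as written, which names no such source.

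Second, 4.6.3 also speaks of COVID-19 disease, and variant is a sensible factor for disease severity among the infected. That is true, but the only dependent variable written is infection.

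Third, the partial-sequencing intervals depend on an assumed rate and on a merged none/unknown category that the SAP does not propose. That is fair. With unknown kept apart from none, separation is again complete; with both groups dropped, the outcome is again constant. The intervals are illustrative and the conclusion does not need them.

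Fourth, the failure would be conspicuous, and SAP section 5 requires program logs to be checked for warnings. That makes an unnoticed failure under full sequencing unlikely. The repair would still be chosen after the data are seen.

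**Conclusion.** The concern holds. With infection as the dependent variable and variant taken from participants' own samples, neither dropping the uninfected nor coding them as having none gives a valid variant odds ratio. Multiple imputation is not available for variant under SAP 4.1.2.

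How far the damage reaches depends on points that 4.6.3 leaves open. With joint entry and all infections sequenced, every term fails. With incomplete sequencing and a merged category, treatment is estimated from a fraction of the infections. With factors fitted one at a time, only the variant model fails.

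The counts assume the planning rates and 138 evaluable per arm; the separation itself does not depend on them. Confidence is medium because a variant definition could sit in text not available here. The point should be corrected but is not critical: the analysis is exploratory, and the primary CMH test, the protocol's logistic regression on treatment and country, and the sample size do not use variant.

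**What to change.** In SAP 4.6.3:

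- Fit infection on treatment, sex, age and BMI, without variant. State the analysis set and whether the factors enter jointly.
- Report variant separately, either descriptively by arm among infected participants or as variant-specific infection by arm with the uninfected as reference.
- Keep variant as a covariate only if it is defined for every participant independently of outcome, for example from the index case, and name that source.

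The cost is wording only, with no new data unless an index-case variant is chosen. The downside is imprecision in variant-specific estimates. If the true odds ratio is 0.43 for every variant, and a variant causes a share s of infections (47qs and 75qs cases against 91 and 63 uninfected), the 95% intervals are:

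| s | All sequenced (q = 1) | q = 0.8 |
|---|---|---|
| 50% | 0.24–0.80 | 0.22–0.84 |
| 25% | 0.20–0.96 | 0.18–1.04 |
| 10% | 0.13–1.44 | 0.11–1.64 |

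Shares and sequencing rates are assumptions; the documents give none.

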4.1.2 Missing data

In general, an observed cases approach will be applied in case of missing data, i.e., only the observed subject data at a given timepoint will be used.

There will be one notable exception to this rule for the primary efficacy endpoint: if a subject discontinued the study without a confirmed negative test result on D28 (and on any day in between), then the missing data will be imputed using a multiple imputation (MI) method, under the assumption that the results are missing at random (MAR). Details on the MI method can be found in section 4.6.1. The MI method will only be used for the primary efficacy endpoint.

Missing/incomplete information related to AEs and concomitant medications will be handled as listed below, when applicable. Following these steps using temporary programming will ensure that missing date imputation uses the most conservative approach.

In case of a (partially) missing onset date, and the end date is determined to be after the first date of study drug administration, the onset date will be imputed as follows:

• Partially missing onset date:

Statistical Analysis Plan	Version 1.0		Page 11 of 25
Sponsor	MedinCell	Protocol No	mdc-TTG-CT-002

- If the day part is missing and month is equal to month of first study drug administration, then day will be set to day part of first study drug administration date.
- o If the day part is missing and month is not equal to month of first study drug administration, then day will be set to the first day of that month.
- o If both day and month part are missing, and year is not the same as the year of the first study drug administration, then day and month will be set to 1 January.
- o If both day and month part are missing, and year is the same as the year of the first study drug administration, then day and month part will be set to day and month of first study drug administration.
- Complete missing onset date:
 - o If the end date is on or after date of first study drug administration, then the onset date will be set to the date of first study drug administration.
 - o If the end date is prior to the date of first study drug administration, then the onset date does not need an imputation, and the event or medication is considered a pre-treatment AE or prior medication.

In case of a (partially) missing end date, the end date will be imputed as follows:

- In case end date is partially missing:

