4.6 Efficacy

4.6.1 Primary endpoint

The primary endpoint is the proportion of laboratory-confirmed COVID-19 infections between baseline and Day 28. Frequency tables will be provided, and individual results will be listed.

For missing results of the primary endpoint, the multiple imputation (MI) method will be used. MI is performed using 3 general steps: imputation, analysis, and pooling. A total of 10 multiple imputations will be generated using a fully conditional specification (FCS) regression. This method conditions on observed values of the primary outcome measured at other time points (including baseline measurements) and possible other covariates that are related to the missing data pattern and/or primary endpoint. Furthermore, imputations will be performed in each treatment group separately and, if applicable, by stratification factor. The statistical model will be applied to each imputed dataset separately. The estimated parameters from the models will then be pooled using Rubin's combining rules. It should be noted that these combination rules rely on the assumption that the estimated

Statistical Analysis Plan	Version 1.0		Page 14 of 25
Sponsor	MedinCell	Protocol No	mdc-TTG-CT-002

statistics are approximately normally distributed, which may not be the case for the underlying data. Normalizing transformations will then be used on the estimated statistics prior to applying Rubin's rules.

The comparison between the two treatment groups of the proportion of participants will be performed using the Cochran Mantel Haenszel (CMH) chi-squared test. Odds-ratio, relative risk and risk differences and corresponding 95% CI will be reported. Country will be used as a stratification factor. In case the study was only performed in one country, the Chi-squared/Fisher's exact test will be used.

This analysis will be performed based on the mFAS and PP population using the planned treatment

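### Read literally, the SAP leaves the exploratory infection model on observed cases while imputing the same outcome for the primary analysis, and its odds ratios are then biased where drop-out differs

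*SAP*

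**What the plan says.** SAP 4.6.1 defines the outcome: "The primary endpoint is the proportion of laboratory-confirmed COVID-19 infections between baseline and Day 28". It then says: "For missing results of the primary endpoint, the multiple imputation (MI) method will be used". Ten datasets are generated by fully conditional specification, separately by arm, and "The statistical model will be applied to each imputed dataset separately" before pooling by Rubin's rules.

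SAP 4.1.2 sets the rule for everything else: "In general, an observed cases approach will be applied in case of missing data", explained as meaning that "only the observed subject data at a given timepoint will be used". It names the primary endpoint as the one exception and closes the list: "The MI method will only be used for the primary efficacy endpoint".

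SAP 4.6.3, under exploratory endpoints, takes sex, age, BMI and variant type as factors that may affect infection. They are to be "assessed with a logistic regression model with proportion of COVID-19 infections as dependent variable and treatment as independent variable", with odds ratios, confidence intervals and p-values. The section states neither a missing-data rule nor an analysis set.

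The Protocol's Schedule of Assessments, note (d), has PCR tests on D1, D4, D7, D10 and D28, and baseline-negative participants are tested "until they become positive or reach the planned end of study".

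**The concern.** The outcome has one-sided missingness. A participant who is positive at D4, D7 or D10 has a final outcome even after leaving. One who leaves still negative has no D28 result, so the outcome is unknown. Under observed cases, all early infections stay in the model and some of the participants who were still negative drop out of it. Whether a participant is retained then depends on the outcome itself. The usual reassurance that complete-case logistic regression is safe when missingness depends only on covariates does not apply.

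At stake is the reading of the 4.6.3 table. Its treatment odds ratio would stand beside the primary one for the same outcome but come from a differently selected set. A covariate linked only to drop-out could be reported as a risk factor for infection.

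**Working it through.** **The plan's own figure.** The Protocol synopsis and SAP 1.4 assume 54% infected on placebo and a 20% difference, with odds ratio 2.28. Taking this as 54% against 34%: (0.54/0.46)/(0.34/0.66) = 1.174/0.515 = 2.28. It reproduces.

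**Inputs not in the documents (assumptions).** The documents give neither the timing of infections nor drop-out by arm.
- Share of placebo infected by D10: 40% or 27%. Ivermectin is scaled by 34/54, giving 25.2% or 17%.
- Drop-out between D10 and D28 among those still negative at D10: 15% in both arms, or 10% on placebo against 20% or 25% on ivermectin.

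**Formula if leavers are dropped.** Let e be the share infected by D10, t the total by D28, c = (t − e)/(1 − e) the later risk, and d the drop-out. The observed odds are

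[e + (1 − e)(1 − d)c] / [(1 − e)(1 − d)(1 − c)].

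Example with e = 0.40 on placebo (c = 0.14/0.60 = 0.233; ivermectin c = 0.088/0.748 = 0.118) and drop-out 10% against 20%:
- Placebo: (0.40 + 0.60×0.90×0.233)/(0.60×0.90×0.767) = 0.526/0.414 = 1.271.
- Ivermectin: (0.252 + 0.748×0.80×0.118)/(0.748×0.80×0.882) = 0.322/0.528 = 0.611.
- Odds ratio: 1.271/0.611 = 2.08.

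For the null case, both arms take the placebo e and c and keep their own d: 1.271/(0.512/0.368) = 0.91.

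| Placebo infected by D10 | Drop-out, placebo / ivermectin | Placebo odds | Ivermectin odds | OR (true 2.28) | OR (true 1) |
|---|---|---|---|---|---|
| 40% | 15% / 15% | 1.327 | 0.582 | 2.28 | 1.00 |
| 40% | 10% / 20% | 1.271 | 0.611 | 2.08 | 0.91 |
| 40% | 10% / 25% | 1.271 | 0.642 | 1.98 | 0.87 |
| 27% | 10% / 20% | 1.239 | 0.580 | 2.14 | 0.94 |
| 27% | 10% / 25% | 1.239 | 0.601 | 2.06 | 0.90 |

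With equal 15% drop-out and 40% infected early, the observed risks rise to 57.0% and 36.8%, but the odds ratio does not move.

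**Why the shift is smaller than the completion ratio.** The ratio of completion among still-negative participants is 0.80/0.90 = 0.889 or 0.75/0.90 = 0.833. Later infections are lost along with the uninfected, which offsets part of this. In the null example, 0.889 × (0.526/0.512) = 0.913.

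**If leavers are scored uninfected.** With n the numerator above, the odds are n/(1 − n). For 40% early and 10% against 20%: (0.526/0.474)/(0.322/0.678) = 2.33, and 2.38 for 10% against 25%. The null values are 1.06 and 1.09. The sign reverses.

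**Covariates.** In a simulated logistic regression (n = 400,000; infections detected 40/30/20/10% at D4/D7/D10/D28; drop-out spread over time), drop-out of 10% against 30% across a covariate with no effect gave it an odds ratio of 1.24. The treatment odds ratio stayed at 2.29 (full data 2.30). With leavers scored negative, the covariate read 0.93.

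**Other timings.** Over three infection-timing and three drop-out-timing profiles, 10% against 20% gave treatment odds ratios of 2.05–2.25, and the reverse (20% placebo, 10% ivermectin) gave 2.31–2.54. The shift is smallest when infections are detected late or drop-out is early.

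**The case against.** **The SAP does not clearly assign observed cases to 4.6.3.** The exception in 4.1.2 could be read as attached to the infection variable, not to one analysis of it. The Protocol synopsis also treats a logistic regression of infection, on treatment and country, as part of the primary endpoint analysis. That reading is possible, but it is not the plain sense of a sentence restricting imputation to the primary endpoint when 4.6.3 sits under a different heading. What stands is that 4.6.3 is silent. The observed-cases rule also speaks of a given timepoint while this outcome spans 28 days, so whether still-negative leavers are lost or scored uninfected is unsettled. A reader might infer a known direction of bias; the documents do not fix one.

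**The size is assumed.** This stands. The documents plan for 30% loss without a split by arm. SAP 1.4 words it as participants not evaluable for the primary analysis, which may include baseline positives, so drop-out within the mFAS may be lower. With 138 per arm, the standard error of the log odds ratio at 54% against 34% is √(1/74.5 + 1/63.5 + 1/46.9 + 1/91.1) = 0.248. That gives a 95% interval of about 1.40–3.70 around 2.28. The shifts to 2.14 and 1.98 are about 0.25 and 0.57 standard errors.

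**Little depends on it.** This also stands. SAP 4.6.2 calls even the secondary analyses explorative. A covariate-adjusted odds ratio would differ somewhat from the country-stratified one in any case.

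**Conclusion.** The point holds as a cheap improvement to an exploratory analysis. The literal default for 4.6.3 is observed cases, the coding of still-negative leavers is unstated, and retention depends on the outcome. If leavers are dropped, under the assumed 10% against 20–25% drop-out, a true treatment odds ratio of 2.28 reads about 1.98–2.14 and a true 1 reads about 0.87–0.94. With equal drop-out there is essentially no bias in the odds ratio.

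Two stronger readings are not supported. One is that every odds ratio in the model is distorted by the completion ratio. Only the odds ratio of a factor linked to drop-out moves materially, and it moves by less than that ratio. The other is that the trial's main result is in doubt. The primary analysis imputes this outcome, and its conclusion is unaffected.

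**What to change.** In SAP 4.6.3, name the mFAS and fit the logistic model on datasets imputed as in 4.6.1, with age, sex and BMI in the imputation model. Pool the log odds ratios by Rubin's rules. Amend 4.1.2 so that imputation covers every analysis of the primary endpoint variable, including 4.6.3. Show the observed-case model as a sensitivity analysis and state there how still-negative leavers are coded.

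The cost is SAP wording and some programming, with one real constraint. SAP 4.6.1 mentions only possible other covariates, so either the primary imputation model is fixed with age, sex and BMI before unblinding, or a separate imputation is run for 4.6.3.

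This does not solve variant type. The Protocol's note (d) ties sequencing to the participant's PCR tests, so variant is likely known only for infected participants, unless the index case's variant is meant. It should be left out of the imputed model and handled separately.
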